- Assuring IRB review and approval
- Preparing and sending reports to the Data Safety Monitoring Board (DSMB)
- Preparing and sending annual reports to the funding agency, the National Institutes of Health (NIH)

B. TRAINING PLAN

The Research Assistant and Study Coordinator will be trained on all clinical assessments by the lead investigators. For all measures, the staff in training should familiarize themselves with the measures and complete mock interviews. The PI will lead all trainings on intervention and control condition delivery.

Interventionist training will include mock session practice and review of audio recorded sessions.

C. STUDY FLOW

D. SCREENING AND ELIGIBILITY TRACKING

How are potentially eligible individuals identified?

Intake nurses will reach out via email to notify when there is a new patient scheduled. We will find a convenient time during that appointment to approach the patient.

How is the screening conducted?

Study staff will use the screening form to determine eligibility.

How do we know which patients to approach for enrollment?

Staff use the following guidelines to determine whether patients are eligible or ineligible to be approached for study enrollment. The majority of the data to determine eligibility are available in the patient medical record; however, for any additional information not available in the medical record, the staff will need to consult with clinical intake staff.

A patient must meet all of the eligibility criteria listed below before they are approached about enrolling in the Engage study.

Table 1. Eligibility criteria

Inclusion Criteria	Exclusion Criteria

 • HIV+ • ≥ 18 years old • Entering HIV medical care services for the first time (that is, not transferring HIV care from another location) • Able to speak and read English at the level to be able to complete the study procedures • Have telephone access 	
 • Cognitive impairment that would interfere with adequate participation in the project (clinic staff will make this determination)

For

each patient screened on that day, the RA will enter the following information into the study Key file:

- ID: A unique screener ID will be generated for all individuals screened
- Date: Date screened

- Name: First *only*
- Telephone number: At least one contact number
- Permission to text appointment reminders: Yes / No
- Permission to leave voicemails for appointment reminders: Yes / No

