Thoughts about PrEP	PROMIS Global Health Scale
Alcohol Use Disorders Identification Test (AUDIT-3)	Health Information
Addiction Severity Index Drug Module (ASI)	Well-Being Scale
Patient Health Questionnaire-9 (PHQ-9)	Impulsivity Scale
Disclosure Scale (BHD & SSSES)	Acceptance and Action Questionnaire-II (AAQ-II)
Disclosure List	Multidimensional Scale of Perceived Social Support (MSPSS)
COVID-19 items	Berger HIV Stigma Scale
	Healthcare System Distrust Scale
	Everyday Experience of Discrimination Scale
	Patient Satisfaction Survey

After the interviews are completed, allow the patient to complete the self-report measures independently (*if possible*). Briefly go over the self-reports with the patient, and ask if they have any questions. **Print all self-reports ONE-SIDED.**

In some cases, participants will consent to be in the study, but will leave the clinic before a baseline appointment can be started and/or completed. If this is the case, arrange a time for them to come complete the baseline appointment within 1 week.

H. POST-BASELINE ASSESSMENT PROCEDURES

After the baseline has been completed, check-in with the PI to verify the patient's eligibility for enrollment and for any questions in assessment/coding that may have arisen. If the PI agrees that the patient is eligible, and no problematic secondary characteristics have been identified that may hinder the patient's participation in the study, the patient is officially enrolled into the study.

Randomization:

Randomization occurs in the REDCap database using information gathered during the baseline interview (participant's depression and substance use scores). See the cover page of the baseline assessment for guidelines. This information can be directly entered into REDCap, which will then generate the allocation.

Follow-Up Assessment Schedule:

Follow-up assessments are conducted at 1-, 3-, 6-, 9-, and 12-months post-baseline. These assessments can be conducted remotely or in-person. All follow-up assessments are audio-recorded.

Measure	Self- Repo rt	1-Mo	3-Mo	6-Mo	9-Mo	12- Mo
Sociodemographics II		X	X	X	X	X
Health Questionnaire (PHQ-9)		X	X	X	X	X
Disclosure Scale (BHD & SSSES)		X	X	X	X	X
Disclosure List		X	X	X	X	X
Self-Rating Scale Item (SRSI)	X	X	X	X	X	X
Contemplation Ladder	X	X				
PROMIS Global Health	X	X	X	X		
Health Information	X	X	X	X	X	X
Well-Being Scale	X	X	X	X	X	X
Acceptance and Action Questionnaire-II (AAQ-II)	X	X	X	X	X	X

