Brief Acceptance-Based Retention Intervention for Newly Diagnosed HIV Patients

NCT04201288

Statistical Analysis Plan – 4/23/19

Data analytic plan (Aim 1).

We will use logistic regression to test the hypothesis that compared with ETAU, ABBT will increase the likelihood of meeting minimum DHHS recommended HIV care. To test the hypothesis that ABBT will result in improved virologic suppression, relative to ETAU, MANCOVA will be used. Planned baseline covariates include age, gender, race-ethnicity, HIV viral load, and study site. Any baseline variables associated significantly ($p < .10$) with subject attrition will also be included as covariates. We will also co-vary for cumulative TAU exposure. A 2-tailed probability of Type I error $< .05$ will be used for all null hypothesis tests.

We will use latent growth models (LGM) to estimate the effect of intervention on ART adherence, disclosure of HIV status, perceived social support, and HIV stigmatization. Data will be available from baseline, 1-, 3-, 6-, 9-, and 12-month follow-ups. This approach offers the flexibility to accommodate outcomes with a range of exponential family (e.g., normal, binomial, etc.) error distributions and allows a comparison of possible alternative growth processes (linear, quadratic, unconstrained with freely estimated time values) describing change over time. Initially, the Satorra-Bentler Scaled Chi-Square⁸⁵ will be used to compare linear change, quadratic change, and models with freely estimated time values. After identifying the best fitting unconditional LGM, conditional LGM models will be estimated in which the intercept and slope growth factors will be regressed on group, age, gender, race/ethnicity, and any baseline measures that significantly ($p < .10$) predict attrition. Significant differences in slope growth factors are consistent with the hypothesis that the ABBT and ETAU arms experience different patterns of change over time.

Data analytic plan (Aim 2).

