The hypothesis that the effects of ABBT will be mediated by increased HIV acceptance and increased willingness to disclose HIV status will be tested in a latent growth model framework⁹¹. We will extend the LGMs estimated when testing the effects of ABBT on secondary outcomes (AIM 1). The slope growth factors in the LGM are latent variables that represent change trajectories which can be used to account for differences in more distal outcomes. For example, the likelihood of meeting minimum DHHS recommended HIV care.

Mediation is tested by specifying an indirect effect defined as the product of the effect of intervention on the slope growth factor of the hypothesized mediator (HIV acceptance, increased willingness to disclose) by the effect of the mediator on meeting DHHS recommended HIV care. Bias-corrected bootstrap resampling is generally recommended for testing the statistical significance of indirect effects⁹². Simulation studies have generally shown this method to be the most efficient method for testing mediational hypotheses^{64, 93}. Mplus⁸² statistical software has facilities to specify and estimate the LGM mediation models.

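### The Aim 1 logistic regression and MANCOVA adjust for cumulative TAU exposure, an undefined and almost certainly post-randomisation variable, so the arm coefficient may not estimate the effect of assignment to ABBT

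*SAP*

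**What the plan says.** The first paragraph of the SAP's Aim 1 plan specifies two tests. For HIV care: "We will use logistic regression to test the hypothesis that compared with ETAU, ABBT will increase the likelihood of meeting minimum DHHS recommended HIV care". For virologic suppression it names MANCOVA. It then gives three sets of covariates:

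- A baseline list: "Planned baseline covariates include age, gender, race-ethnicity, HIV viral load, and study site".
- Baseline variables that predict attrition at p < .10.
- A separate item: "We will also co-vary for cumulative TAU exposure".

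The third item has no definition, unit, data source or time window in either document, and it is not called a baseline variable. No version of the two tests without it is described.

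The latent growth models in the next paragraph have their own covariate list, which omits TAU exposure: "the intercept and slope growth factors will be regressed on group, age, gender, race/ethnicity, and any baseline measures". They are not affected.

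Two statements in the Protocol bear on timing. Table 1 requires participants to be "Entering HIV medical care services for the first time (that is, not transferring HIV care from another location". Section H says: "Randomization occurs in the REDCap database using information gathered during the baseline interview". Follow-up then runs to 12 months.

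**The concern.** Randomisation protects a comparison that is adjusted only for variables fixed before allocation. Adjusting for something that assignment may change loses that protection in two ways. It removes any part of the effect that runs through the variable. It also opens a non-causal path if the variable and the outcome share unmeasured causes, such as engagement or need.

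ABBT is, by the trial's title, a retention intervention, and one outcome is receipt of recommended HIV care. An effect of ABBT on usual-care contact is therefore plausible, although the documents do not assert one. The mediators named in the SAP's Aim 2 plan are different: "hypothesized mediator (HIV acceptance, increased willingness to disclose". If TAU exposure counts HIV clinic visits, it could also overlap with the visits that make up the DHHS outcome. Without a definition this cannot be settled.

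The Aim 2 text calls the latent growth outcomes secondary, which implies that these two tests carry the main Aim 1 hypotheses. The adjusted result could understate the effect, overstate it, or reject too often when there is none. The plan gives the reader no means of telling which has happened.

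**Working it through.** **Timing, from the text.** The variable is placed outside both baseline groups and is described as cumulative. Participants have no previous HIV care from which exposure could build up. Allocation follows the baseline interview, with 12 months of follow-up after it. Accrual after randomisation is the natural reading, though it remains an inference.

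**Size.** The documents give no sample size, event rate or effect size, so there is no figure to reproduce. All inputs below are assumptions.

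Model: A = arm (1:1); U = unmeasured common cause; U and e are independent N(0,1).

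- TAU exposure: T = d·A + 0.6U + 0.8e
- Outcome: logit P(Y=1) = direct·A + bT·T + bU·U, with intercept 0, so the control-arm rate is about 50%.

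The arm odds ratio (OR) and standardised risk difference (RD, percentage points) were estimated without and with T in the logistic model, at 2,000,000 subjects per scenario.

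| Scenario | d | direct | bT | bU | OR without → with T | RD without → with T |
|---|---|---|---|---|---|---|
| ABBT raises TAU; engagement drives both | 0.3 | 0.4 | 0.8 | 0.5 | 1.65 → 1.35 | 12.3 → 6.0 |
| Effect acts wholly through TAU | 0.5 | 0 | 0.8 | 0 | 1.42 → 1.00 | 8.6 → 0 |
| Need drives TAU use and worse outcome | 0.3 | 0.8 | 0 | −0.8 | 2.02 → 2.38 | 16.9 → 19.9 |
| ABBT lowers TAU | −0.3 | 0.5 | 0.5 | 0.5 | 1.35 → 1.76 | 7.3 → 12.4 |
| TAU unrelated to outcome | 0.3 | 0.8 | 0 | 0 | 2.2 → 2.2 | no shift |
| Assignment does not change TAU | 0 | 0.6 | 0.8 | 0.5 | 1.60 → 1.79 | 11.6 → 11.6 |

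In the last row the OR moves only because odds ratios are non-collapsible; the RD shows no bias. Opposing paths can also cancel.

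**No effect of ABBT on the outcome** (direct = bT = 0, bU = 0.8). The adjusted OR is 0.80 for d = 0.5 and 1.25 for d = −0.5, where the truth is 1.00. The two-sided 5% test with T rejects in 7–8%, 11% and 18–19% of 6,000 replicates at N = 100, 200 and 400, against 5–6% without T.

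**Power**, without → with T, at N = 100/200/400:

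- ABBT raises TAU: 26/43/70% → 11/15/26%.
- Need scenario: 42/70/93% → 53/83/99%.
- ABBT lowers TAU: 13/19/34% → 25/45/75%.

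**Linear outcome** (for the MANCOVA, in error-SD units). Given A, the slope of U on T is 0.6/(0.6² + 0.8²) = 0.6. Hence:

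- total effect = direct + bT·d
- coefficient adjusted for T = direct − 0.6·bU·d

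Two examples:

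- d = 0.3, direct = 0.2, bT = 0.4, bU = 0.25: total 0.2 + 0.4 × 0.3 = 0.32; adjusted 0.2 − 0.6 × 0.25 × 0.3 = 0.155.
- d = −0.3, direct = bT = bU = 0.25: total 0.25 − 0.25 × 0.3 = 0.175; adjusted 0.25 + 0.6 × 0.25 × 0.3 = 0.295.

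**Cross-check with a separate set of assumptions.** Here T has unit SD within arm, and the direct effect is 0.4 log-odds with no common cause. The OR goes from 1.62 to 1.47 when ABBT shifts TAU by 0.25 SD and TAU acts at 0.5 log-odds per SD, and from 1.84 to 1.49 when the shift is 0.5 SD. With no effect on the outcome and a common cause of strength 0.5, the adjusted OR is 0.94 or 0.89 for shifts of 0.25 or 0.5 SD. The conclusion is the same, with milder figures under no effect.

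**The case against.** The strongest reply has four parts.

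- **Timing and definition.** The timing is inferred. TAU is not described in these documents, and if it includes services other than HIV care, some exposure could predate allocation. The Protocol also says that it supplements another protocol document, which might define the term. This is fair, but it does not remove the problem: the SAP should define its own covariates, and if a pre-randomisation measure is meant, the text must say so.
- **Conditional bias.** Distortion requires that ABBT changes TAU exposure, and that this exposure affects the outcome or shares causes with it. The documents do not claim the first. This stands, and the no-bias rows show it. But the plan includes neither an analysis without the covariate nor a report of TAU exposure by arm, so readers could not tell which case applies.
- **False-positive rates.** These are an upper-end case. Reruns with 3,000 replicates at N = 100/200/400 gave 5.4/7.1/8.4% with d = 0.25, 5.0/5.6/5.4% with d = 0.1, and 5.2/6.0/8.8% with d = 0.5 and bU halved to 0.4. This stands. The case for change should rest on the effect of assignment no longer being what is estimated, not on those rates.
- **Omitted covariates.** The simulation leaves out the planned baseline covariates, which could absorb part of the common cause. That would reduce the non-causal path, but it would not restore an effect lost through TAU exposure.

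It could also be argued that adjustment evens out differences in outside care. That targets a different quantity from the effect of assignment, and it would still need control of the common causes of TAU use and outcome, for which nothing specific is planned.

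**Conclusion.** The concern holds and should be fixed before analysis. Both Aim 1 tests are exposed; the latent growth models are not. The direction and size of any bias cannot be computed from the documents. Under the assumed inputs, adjustment can halve a risk difference (12.3 to 6.0 points), remove it (8.6 to 0) or inflate it (7.3 to 12.4), and it does no harm if assignment leaves TAU exposure unchanged. The conclusion rests on reading the covariate as accruing after randomisation, which the text strongly favours, and on the plausible but unstated possibility that a retention intervention alters usual-care contact.

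**What to change.** - Restrict the main logistic regression and MANCOVA to covariates measured before randomisation: the listed baseline variables and the baseline predictors of attrition.
- Define TAU exposure: what is counted, in what units, from which source and over what window. State whether it overlaps with the visits that count toward the DHHS outcome.
- Report TAU exposure by arm.
- If a TAU-adjusted model is still wanted, keep it as a labelled sensitivity or mediation analysis and state its assumptions about common causes of TAU use and outcome.

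The cost is one SAP sentence changed and one definition added. No new data are needed.

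### Study site is a fixed covariate in the logistic and MANCOVA models but not in the Aim 1 growth models: a modest loss of precision there, and a possible confounder once Aim 2 extends them

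*SAP*

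**What the plan says.** SAP, Data analytic plan (Aim 1), first paragraph, on the logistic regression and MANCOVA: "Planned baseline covariates include age, gender, race-ethnicity, HIV viral load, and study site". The same paragraph adds "We will also co-vary for cumulative TAU exposure".

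Second paragraph: latent growth models are used "to estimate the effect of intervention on ART adherence, disclosure of HIV status, perceived social support, and HIV stigmatization". In the conditional models, "the intercept and slope growth factors will be regressed on group, age, gender, race/ethnicity", together with "any baseline measures that significantly" predict attrition, at p < .10. Study site, baseline viral load and usual-care exposure are not on this list, and the difference is not explained.

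SAP, Data analytic plan (Aim 2): the mediation models extend these growth models. The indirect effect is the arm effect on the mediator slope multiplied by the mediator's effect on meeting the recommended HIV care. No covariates are restated.

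Protocol (Manual of Procedures), section H, Randomization: allocation is made in REDCap "using information gathered during the baseline interview (participant's depression and substance use scores"). It continues: "This information can be directly entered into REDCap, which will then generate the allocation". Site is not named among the inputs, and the reader is referred to guidelines on the baseline cover page, which is not part of the documents.

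**The concern.** Naming site as a covariate implies that the SAP expected more than one site and thought site might be prognostic. One paragraph later, whether site is adjusted for depends on a significance test of attrition. That test does not address whether site predicts adherence, disclosure, support or stigma.

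Two things are at stake. In Aim 1, any variation in the growth factors between sites stays in the residual and widens the interval for the arm difference in slopes. In Aim 2, the mediator is not randomised. If sites differ both in how acceptance or willingness to disclose changes and in how often the care standard is met, part of the association between mediator and care is due to site.

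**Working it through.** **Inputs.** The documents give no sample size, power, number of sites or site difference, so there is no stated figure to reproduce. The following are assumptions: two equal sites (p = 0.5); individual 1:1 allocation not stratified by site; site difference d in the growth factor of 0.25, 0.5 or 1.0 within-site SD; total N of 60, 100 or 200. Two-sided alpha of 0.05 is from the SAP. A two-arm comparison of means stands in for the slope contrast; no full growth model was fitted.

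**Bias and type I error in Aim 1.** In 20,000 simulated trials per combination, analysed without site, the mean error in the arm contrast lay between -0.001 and 0.002 SD. Type I error lay between 0.047 and 0.052. There is no systematic bias and the test keeps its level.

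**Precision in Aim 1.** Without site, residual variance rises from 1 to 1 + d²p(1-p).
- At d = 0.5: 1 + 0.25 × 0.25 = 1.0625. The standard error ratio is √1.0625 = 1.031, or about 3% larger. Site explains 0.0625/1.0625 = 5.9% of the variance.
- An effect with 80% power when site is adjusted for lies 1.960 + 0.842 = 2.802 standard errors from zero. Without site, power is Φ(2.802/1.031 - 1.960) = Φ(0.758) = 77.6%.
- The same calculation gives 79.4% at d = 0.25 and 70.7% at d = 1.0. N does not matter here, because the effect is scaled to 80% power.
- With one site, d²p(1-p) = 0 and nothing is lost.

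**Chance imbalance is the same cost, not a second one.** The SD of the shift from unequal site shares is d√(p(1-p) × 4/N). At N = 100 and d = 0.5 this is 0.5 × 0.100 = 0.050 SD. The standard error of the site-adjusted contrast is √(4/100) = 0.200, and (0.050/0.200)² = 0.0625. This is exactly the variance increase above, so the unadjusted standard error already allows for the shift.

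**If allocation is stratified by site.** Site shares are then nearly equal between arms, but a model without site still uses the larger residual variance. At d = 0.5 the effective critical value is 1.960 × 1.031 = 2.02, so the true two-sided level is about 0.043 instead of 0.05: slightly conservative.

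**Aim 2.** Suppose two equal sites differ by 0.5 SD, in the same direction, in both the mediator slope and the propensity to meet the care standard. Site alone then creates a covariance of 0.25 × 0.5 × 0.5 = 0.0625 SD² between them. Divided by the mediator variance of 1.0625, the mediator-to-care coefficient moves by about 0.059 on a linear propensity scale. The indirect effect moves by 0.059 times the arm effect on the mediator. Unlike the Aim 1 cost, this is systematic and does not shrink with sample size.

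**The case against.** The strongest reply is that this hardly matters for Aim 1. Participants are individually randomised, so site is independent of arm in expectation. The loss is about 3% of a standard error on secondary outcomes, and only if sites differ in rate of change. Stable differences in level between clinics load on the intercept factor, not on the slope factor from which the SAP draws its inference, and nothing in the documents supports a 0.5 SD difference in slopes. The manual also reads in places like a single-clinic study: it speaks of the clinic in the singular and uses one numbering series. All of this stands and limits the weight of the point. It does not settle the number of sites, because the SAP lists site as a covariate and the manual refers to an institution-specific tracking log and a centralized database.

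A reader might go further and infer that differences in background care between sites confound the ABBT-versus-ETAU comparison. The documents do not support this. Neither describes usual care or says that it varies by clinic. The manual names "depression and substance use scores" as allocation inputs, but it does not say that these are the only ones. It describes itself as a supplement to a protocol that is not among the documents, so stratification by site is neither stated nor excluded. Even without stratification, randomisation leaves only chance imbalance.

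It is also fair to say that adding site alone does not make the two lists identical, since viral load and usual-care exposure differ too. The gain from site does not depend on resolving those. Cumulative usual-care exposure appears to accrue after allocation, so whether to adjust for it is a separate question.

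What the reply does not reach is Aim 2: randomisation of arm gives no protection to the mediator-to-care path.

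**Conclusion.** The inconsistency is plain in the text and unexplained. In Aim 1 it is a precision point of modest size: at an assumed 0.5 SD site difference in the growth factor with two equal sites, the standard error is about 3% larger and power about 77.6% instead of 80%. Over assumed differences of 0.25 to 1.0 SD, power is 79.4% to 70.7%. The cost is nil with one site, and the tests are slightly conservative if allocation is stratified by site. It does not amount to bias in the Aim 1 arm contrast. For growth models with a binary outcome, which the SAP allows, omitting site also changes the conditional effect being estimated, so those results are not on the same footing as the site-adjusted logistic model.

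In Aim 2 the omission could confound the mediator-to-care path, on condition that more than one site enrols and site affects both the mediator and care. The documents neither establish nor rule out that condition. The point is worth acting on mainly because the remedy costs so little.

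**What to change.** In the SAP, Data analytic plan (Aim 1), name study site as a fixed covariate on the intercept and slope factors of the conditional growth models, whether or not it predicts attrition. In Data analytic plan (Aim 2), state that site is carried into the mediation models as a predictor of both the mediator's growth factors and the care outcome. If site is left out on purpose, give the reason. It would also help to state how many sites enrol and whether the REDCap allocation is stratified by site.

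The cost is a phrase in each section and one parameter per growth factor per additional site, plus the same for the Aim 2 outcome. No new data should be needed, because the SAP already plans to use site in the logistic and MANCOVA models. If only one site enrols, the term simply falls away.

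### The growth models free the group effect on the intercept, although randomisation makes it zero in expectation for outcomes measured at baseline; this costs slope precision and can divert part of an early effect

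*SAP*

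**What the plan says.** The SAP (Data analytic plan, Aim 1) uses latent growth models for "ART adherence, disclosure of HIV status, perceived social support, and HIV stigmatization". Baseline is one of the six repeated measures: "Data will be available from baseline, 1-, 3-, 6-, 9-, and 12-month follow-ups". The growth shape is settled first, by a scaled chi-square used to "compare linear change, quadratic change, and models with freely estimated time values". Group enters only at the next step: "After identifying the best fitting unconditional LGM", the SAP fits conditional models in which "the intercept and slope growth factors will be regressed on group" together with covariates. The treatment effect is read from the slope alone: "Significant differences in slope growth factors are consistent with the hypothesis" that the arms change differently. The SAP does not say where time zero is placed, and it mentions no constraint on the group effect on the intercept.

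The protocol (section H, Randomization) fixes the order of events: "Randomization occurs in the REDCap database using information gathered during the baseline interview". The baseline schedule in section G lists the disclosure scale, the perceived social support scale and the HIV stigma scale. No instrument in it is labelled as ART adherence.

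Aim 2 of the SAP builds its mediation test on the same models. The first leg of each indirect effect is the intervention effect on the mediator's slope.

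**The concern.** Allocation follows the baseline interview, so any arm difference in a baseline measure is chance. With time coded 0 at baseline, the intercept is the model's baseline level, and the group effect on it has a known expected value of zero. The plan estimates this quantity and then sets it aside.

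There are two consequences:

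- **Precision.** With the path free, the slope contrast behaves like a comparison of change from baseline. With the path fixed at zero, baseline acts as an adjustment variable, as in ANCOVA. The first cannot be more precise than the second and is usually less so.
- **Attribution.** If the fitted curve cannot follow an effect that appears early and then holds, the model absorbs part of it as a baseline difference. That part drops out of the slope, which is the only parameter interpreted.

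The second matters because the trial's title calls the intervention brief, and the end-of-treatment questionnaire is scheduled at month 1 only. An effect largely in place by month 1 is plausible.

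**Working it through.** The documents give no sample size, effect size, SD or power, so there is no planned figure to reproduce. The variance inputs below are assumptions.

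**Inputs from the documents.** Visits at months 0, 1, 3, 6, 9 and 12; two-sided 0.05; intercept and slope both regressed on group; slope alone tested.

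**Assumed inputs.** Baseline variance 1; reliability (intercept share of baseline variance) 0.6; SD of 12-month slopes 0.5; intercept-slope correlation -0.2; linear shape; normal outcome; complete data; equal arms; no covariates.

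**Step 1: information matrix.** Let L hold a column of ones and a column of months/12. The growth-factor covariance matrix P has variances 0.6 and 0.25 and covariance -0.2 × √0.6 × 0.5 = -0.077. The outcome covariance is S = L P L' + 0.4 × identity. Then I = L' S⁻¹ L has entries I11 = 1.550, I12 = 0.607 and I22 = 1.537.

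**Step 2: slope-effect variance (up to a common factor).**

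- Path free: I11 / (I11 × I22 - I12²) = 0.770.
- Path fixed: 1 / I22 = 0.651.
- Ratio: 0.651 / 0.770 = 0.846, a reduction of 15%.

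This equals 1 / 0.846 = 1.18, or about 18% more participants. For a truly linear effect with 80% power, the test statistic's mean of 1.960 + 0.842 = 2.802 becomes 2.802 / √0.846 = 3.047, and power becomes Φ(3.047 - 1.960) = 0.86.

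**Step 3: range.** At reliability 0.6 and slope SD 0.5, the reduction depends on the intercept-slope correlation:

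| Correlation | Variance reduction |
|---|---|
| -0.2 | 15% |
| 0 | 8.5% |
| +0.2 | 3.6% |
| +0.3 | 2.0% |

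Over reliability 0.5 to 0.8 and slope SD 0.3 to 0.7, it is 2% to 28% for correlations from -0.4 to 0, and 0% to 11% for correlations from +0.2 to +0.4.

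**Step 4: an early, sustained effect.** Take 0.40 SD at every visit from month 1. The generalised least squares fit of a line gives:

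- Path free: intercept 0.237, slope 0.224. The intercept takes 0.237 / 0.40 = 59% of the effect.
- Path fixed: slope 0.224 + (0.607 / 1.537) × 0.237 = 0.317.

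At an illustrative 75 per arm, the standard errors are √(2 × 0.770 / 75) = 0.143 and √(2 × 0.651 / 75) = 0.132. Power is 0.35 with the path free and 0.67 with it fixed.

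**Step 5: other shapes.** For a 0.5 SD effect complete by month 1, the amount credited to the intercept with the path free is:

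| Fitted shape | Credited to intercept |
|---|---|
| Linear | 0.296 (59%) |
| Quadratic | 0.194 (39%) |
| Free loadings fitted to a pooled trend (linear control trend plus the effect) | 0.162 (32%) |
| Free loadings matching the effect | 0 |

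A truly linear effect under a linear model also leaks nothing. The precision cost does not depend on mismatch. At zero intercept-slope correlation and intercept share 0.4 to 0.8, it is 7% to 25% for the linear term of the quadratic model and 6% to 39% with matching free loadings.

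**Step 6: type I error.** In 200,000 simulated trials with no effect, the rejection rate was 0.0497 with the path free and 0.0495 with it fixed.

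**The case against.** The strongest reply is that the planned specification is valid. Regressing both growth factors on group is a legitimate model, the slope test holds its level, and it is unbiased when the shape is right. The outcomes concerned are ones the SAP itself calls secondary. All of that stands: this is a matter of efficiency and interpretation, not an error that invalidates a result.

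The size of the gain also rests on inputs the documents do not supply, and positive intercept-slope correlations can reduce it to nothing. That stands too, which is why the range starts at 0%.

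Next, the SAP does not commit to a straight line. Quadratic and free-loading shapes reduce the diversion of an early effect and can remove it. This stands in part. The shape is chosen in the unconditional model, before group enters, so it follows the pooled trajectory and need not fit the difference between arms.

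Finally, the constraint is not free of drawbacks. It does not cure a wrong shape: the 0.40 step effect is still estimated as 0.32. Suppose an effect is 0.40 at months 1 and 3 and then declines linearly to zero at month 12. At the central values the linear slope moves from about -0.19 (free) to -0.08 (fixed), so the test has less to detect. The drawback is small, because the signal lost is a negative slope for an effect that was beneficial throughout.

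**Conclusion.** The point holds as one of power and interpretation for the growth-model outcomes measured before randomisation, and for the intervention-to-mediator path in Aim 2 where the mediator has a baseline measure. The variance saving lies between 0% and 28% in the linear case. The diversion of an early effect is substantial only when the fitted shape misses it. Both figures depend on assumed variances and correlations, normal outcomes, complete data and time coded 0 at baseline.

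A reader might infer more than the documents support:

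- That baseline data are thrown away. They are not; baseline remains in the likelihood. What is lost is the precision gained from knowing that the arms are equal in expectation at that time.
- That the plan risks false positives. It does not; type I error is nominal either way.
- That the main conclusions are exposed. The logistic test of HIV care and the MANCOVA of viral suppression do not use these models.
- That an early effect must leak into the intercept. It need not, given the alternative shapes the SAP allows.

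The change is worth making because it is cheap and valid under randomisation, and its gain ranges from negligible to material.

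**What to change.** Amend the conditional-model paragraph of the SAP (Aim 1) to:

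1. State that time is coded 0 at baseline.
2. Fix the group-to-intercept path at zero for every outcome with a pre-randomisation measure (disclosure, perceived social support, HIV stigma), and keep the covariate-to-intercept paths.
3. Leave the path free for any outcome without such a measure. ART adherence appears to be one, since the baseline schedule names no adherence instrument; the SAP should say which measure is used and when it is first taken.
4. Report the free-path model as a sensitivity analysis.
5. Apply the same rule to the mediator models in Aim 2.

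Because the constraint does not repair a wrong growth shape, a prespecified joint test of the growth factors or a model-based 12-month contrast would be a useful complement.

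The cost is a few lines in the SAP and one fixed parameter per model. No extra data or participants are needed. The one drawback is the weaker linear slope contrast for an effect that fades by month 12, which the sensitivity analysis would show.
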